6.0 Evaluation During Study

Patients will be evaluated at 1, 2, 3, and 4, and 8 weeks following completion of radiation therapy by telephone, fax, or mail. Patients will be seen for follow up visits at 3, 6, 9, 12, 18, and 24 months and then every six months thereafter; History, neurological exam, and neurologic function according to the McCormick scale will be assessed. MRI of the spine will be obtained at 3, 6, 9, 12, 18, and 24 months and then every six months thereafter. Included in the appendices, the Brief Pain Inventory (BPI) (Short Form), MD Anderson Symptom Inventory (MDASI) and SF-12v2 Health Survey will be administered at each clinic and telephone follow up. Pain medication requirements will be recorded on the BPI.

The BPI is a 17 item patient self rating scale assessing demographic data, use of medications, as well as sensory, and reactive components of pain (5). Reliability has been demonstrated over short intervals using test retest item correlation; worst pain, r=0.93; usual pain, r=0.78; pain now, r=0.59. The BPI includes items that will address components of sensory pain including severity, location, chronicity and degree of relief due to therapy. The BPI also has items that address reactive pain components including depression, suffering and perceived availability of relief.

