7.0 Criteria for Response

Pain, Symptom and Quality of Life Instruments

Frequency and duration of complete pain relief will be the primary endpoint for efficacy of the study. The validated Brief Pain Inventory (BPI), MD Anderson Symptom Inventory (MDASI), and SF-12v2 Health Survey will be used to assess changes in these indicators compared to pre-treatment baseline. Response will be determined by follow-up questionnaires. Time to maximal pain relief will be the time from the first day of irradiation until the lowest pain score for average pain after radiotherapy. The "worst pain score" from BPI will be used as the marker for treatment success or failure.

Treatment Failures

All the following are considered treatment failures:

- 1) A pain score greater than 0 that does not change within 8 weeks from start of radiation therapy.
- 2) A 2 point increase in "worst pain score" that is sustained at a higher level in the month following the first day of radiation therapy.
- 3) A pain score that drops by at least 2 points and subsequent sustained rise (on 2 successive questionnaires) of pain score by at least 2 points.

Pain Relief

- 1) Patients experiencing a decrease of 2 points in the worst pain score for 2 consecutive analysis periods will be considered to have "partial pain relief."
- 2) Complete pain relief is defined as an average pain score of 0 for 2 consecutive analysis periods.

Radiographic Assessments.

MRI of the spine will be performed according to standard of care. These data will be collected on treated lesions and will be classified as progressive defined as larger, stable defined as radiographically unchanged, or smaller.

The date of radiological progression will be recorded. Progression free survival based on time to event curves will be calculated.

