8.0 Criteria for Removal from the Study

Toxicity monitoring will be focused on neurological, gastrointestinal, musculoskeletal, hematologic, and dermatologic systems. Toxicity will be graded according to NCI toxicity scale. Patients who have evidence of disease progression will be noted as tumor progression on the date progression is observed. Patients will be seen according to the follow up schedule for toxicity monitoring until death unless they withdraw consent for participation in the study in which case they will be removed from the study. For patients unable to return for follow-up clinic visits due to progressive disease or illness, these patients will be monitored via telephone follow-up until time of death.

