Properties of the Design Assuming Other Values of p

Quit If Evidence That $\Theta > H_0$

Prob Event	Prob Quit	Expected N	Expected N Given Quit
0.0500	0.6381	43.06	33.45
0.1000	0.9566	27.67	26.21
0.1500	0.9969	20.76	20.64
0.2000	0.9998	17.70	17.69

RESPONSE RATE

Assuming that safety concerns are met, the purpose of the trial is to estimate the response (pain relief) rate. All 60 patients entered will be used for this purpose.

Tumor control will be based on spinal MRI showing absence of progression. Actuarial and crude rates of tumor control will be calculated.

Pain relief will be assessed by items on the BPI that measure severity, location, chronicity, and degree of relief due to therapy by demographic data that will track use of narcotic and non-narcotic pain medications. For previously unirradiated patients as are in this trial, 46% of patients should demonstrate complete sensory pain relief and 90% should have some pain relief reported as a decrease in severity rating and use of pain medications and increase in the pain relief rating (Blitzer 1985).

The expected change in these indicators should occur within 1 month from the end of radiation therapy based on experience with 3 fraction SBRT on protocol ID02-446. Forty percent of patients should demonstrate complete sensory pain relief by 6 months from the end of radiation therapy as reported by the same indicators. Duration of sensory pain relief should approach a mean of 24 weeks for those patients reporting some relief and 13 weeks for those patients reporting complete relief. For patients surviving one year or more, 60% should report sustained relief based on results with standard radiation therapy.

Pain, Symptom and Quality of Life Instruments

The MD Anderson Symptom Inventory (MDASI) is a measure of symptom severity and symptom interference while the SF-12v2 Health Survey is a measure of health status. Because changes in symptom severity are usually associated with changes in health status, we are interested in assessing the relationship of symptom severity and symptom interference on health-related functional status of life using the SF12's physical and mental component scores. We will regress the MDASI with the component scores of the SF12 and examine the overlap in variability between the measures.

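### Time to maximal pain relief requires no relief from baseline and has no time window or tie rule, so a patient who only worsens is recorded at the earliest possible time

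*Combined protocol and SAP*

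**What the plan says.** The whole definition is one sentence in section 7.0, Criteria for Response, which sets time to maximal pain relief as "the time from the first day of irradiation until the lowest pain score for average pain after radiotherapy". It names a start, an item (average pain) and an end (the minimum). It names no reference score, responder condition, last eligible assessment, rule for a repeated minimum, or handling of death, withdrawal or missed questionnaires.

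The assessment times are in section 6.0. "Patients will be evaluated at 1, 2, 3, and 4, and 8 weeks following completion of radiation therapy by telephone, fax, or mail", and then "Patients will be seen for follow up visits at 3, 6, 9, 12, 18, and 24 months and then every six months thereafter". The BPI "will be administered at each clinic and telephone follow up". No end date for pain assessment is given.

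Three other places bear on the point:

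- Section 7.0 says of the three questionnaires that they "will be used to assess changes in these indicators compared to pre-treatment baseline". This is a general statement and not part of the time definition.
- Section 8.0 says: "Patients will be seen according to the follow up schedule for toxicity monitoring until death unless they withdraw consent". This concerns toxicity, on the same schedule.
- Section 9.0 repeats the failure and relief rules but gives no analysis for this measure. Section 3.0 sets no minimum baseline pain for entry.

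**The concern.** The measure is named for relief but calculated from the lowest score alone. Three consequences follow from the wording:

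- **Non-relief receives a time.** If average pain only rises, the lowest post-treatment score is the first one, so the patient is recorded at week 1. The same patient may be a treatment failure under section 7.0, but failures are not excluded from the measure.
- **The search has no end.** Each further questionnaire is another chance for a new minimum, so a patient who lives longer can be given a later time for the same pain course. Section 6.0 itself quotes a test-retest correlation of 0.78 for usual pain, against 0.93 for worst pain. If usual pain stands for the average-pain item, chance minima are realistic.
- **Ties are unresolved.** Repeated equal scores, including the repeated zeros the trial hopes for, give no single date.

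At stake is the interpretation of the only measure of speed of relief defined in section 7.0. A short average could reflect prompt relief, patients who were never relieved, or short follow-up.

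**Working it through.** The plan states no expected value, power or sample size for this measure, so there is no figure to reproduce. The check applies the definition to the section 6.0 schedule.

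**Inputs.** Assessments are at weeks 1, 2, 3, 4 and 8 and months 3, 6, 9, 12, 18 and 24, taken as weeks 13, 26, 39, 52, 78 and 104. Treatment is a single session, so its first day and its completion coincide.

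**Step 1: worked patients, weeks 1, 2, 3, 4, 8** (scores chosen for illustration).

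| Baseline | Scores | Recorded time |
|---|---|---|
| 4 | 5, 6, 7, 8, 9 | 1 week |
| 7 | 6, 5, 4, 3, 1 | 8 weeks |
| 5 | 5, 5, 5, 5, 5 | 1 week (first tie) or 8 weeks (last tie) |
| 6 | 4, 2, 0, 0, 0 | 3 weeks (first tie) or 8 weeks (last tie) |

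The patient who never improved has the shortest time. The third and fourth rows depend on a rule that the plan does not give.

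**Step 2: follow-up length, simplest illustration.** Assume the minimum is equally likely at each assessment. The mean time is then the average of the assessment weeks.

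- To month 3: (1 + 2 + 3 + 4 + 8 + 13)/6 = 31/6 = 5.2 weeks.
- To month 24: (31 + 26 + 39 + 52 + 78 + 104)/11 = 330/11 = 30 weeks.

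**Step 3: simulated pain courses** (200,000 patients per profile). Assumed: baseline 6, visit noise SD 1, scores rounded and kept within 0 to 10, first tie counts, and six-monthly visits continued to week 208.

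- Responders settling at a mean of 2 have a median time of 4, 8, 13, 26 and 39 weeks when followed for 8, 26, 52, 104 and 208 weeks.
- With exponential survival of median 13, 26, 52 and 104 weeks, the responder mean is 7.9, 13.1, 22.2 and 33.6 weeks for the same pain course.
- Worsening patients have a median of 2 weeks at every fixed follow-up length, with 49 to 50% recorded at week 1.

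**Step 4: would a simple repair be enough?** Keep baseline 6 and SD 1, and take a patient whose true pain is unchanged.

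- *Any score below baseline.* One rounded score is at or above baseline with probability 0.691. Over the seven visits to month 6, the chance of at least one lower score is 1 - 0.691^7 = 0.92. This condition excludes almost nobody.
- *A single 2-point drop within 3 months.* The simulation admitted 34% of unchanged and 9.7% of worsening patients.
- *A 2-point drop at two consecutive visits to month 6.* One score is 2 or more points down with probability 0.0668 (noise below -1.5). There are six adjacent pairs, so the chance is at most 6 x 0.0668^2 = 0.027.
- *A 6-month cap.* Under Step 2's assumption, follow-up to week 8 gives 18/5 = 3.6 weeks and to week 26 gives (31 + 26)/7 = 8.1 weeks. The dependence on follow-up shrinks but remains.

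**The case against.** The strongest reply is that the measure decides nothing. The primary efficacy endpoint in section 7.0 is complete pain relief, and section 9.0 judges success on the 1-month responder proportion using worst pain. No test, sample size or stopping rule uses time to maximal relief. That stands, and it limits the weight of the point.

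A second reply is that maximal relief presupposes relief and that section 7.0 mentions comparison with baseline. That may well be the intention, but no sentence restricts the calculation to relieved patients.

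A third reply is that scores stop at 0. A patient who reaches 0 early keeps that date under a first-occurrence rule, however long the survival. Section 9.0 expects 46% to reach complete relief. This also stands: the dependence on survival applies to patients who do not reach 0 early, or if the last tie counts.

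Four stronger readings are tempting, and the documents do not support them:

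- A reader might infer that the plan loses its check on the expectation that "The expected change in these indicators should occur within 1 month from the end of radiation therapy". Those indicators are severity rating, medication use and relief rating, and the sentence concerns change, not the minimum. The 1-month responder rule examines that timing better.
- A reader might turn the expected 90% with some relief into 6 of 60 patients with a spurious time. That 90% is not on the scale of average pain below baseline, and not every patient need enter with pain.
- A reader might rest the open-ended search on the until-death wording in section 8.0. That wording is about toxicity; the search rests on section 6.0.
- A reader might conclude that worsening patients look faster than every responder. They are tied with a responder whose lowest score is at week 1.

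**Conclusion.** The point holds as a gap in the definition of a supporting descriptive measure. That a patient whose average pain only rises is recorded at the earliest assessment follows from the wording alone and needs no assumption. That the time can lengthen with follow-up and survival needs scores that can still reach a new minimum later. Its direction is clear, but its size is not known from the documents. The 5 against 30 weeks requires an equally likely minimum at each visit, and the simulated figures require the assumed profiles, noise and survival. The primary endpoint, the 60-patient sample size and the safety stopping rule are unaffected. The definition should be tightened before the measure is reported, because as written a short time cannot be read as prompt relief.

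**What to change.** Replace the sentence in section 7.0 with a definition that does the following:

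1. Calculates the time only for patients with baseline pain above 0 who meet section 7.0's partial or complete relief definition, each of which needs two consecutive analysis periods. Define an analysis period. Partial relief uses worst pain while the time uses average pain, so state this, and also require the lowest average score to be below its own baseline.
2. Uses the first date of the lowest average pain score within a fixed window, for example the 6 months that section 9.0 already uses for complete relief.
3. Reports all other patients as having no relief, with a count and no time.
4. Reports how many patients died or were lost before the window closed, and adds the cumulative incidence of first sustained relief with death as a competing event.

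**Cost.** No new data are needed; the BPI is already collected at every contact. The change is one rewritten definition and a small extra analysis. Minima after the window are not counted. Some dependence on survival within the window remains and should be stated with the result.

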9.0 Statistical Considerations

The advantage of stereotactic radiation given in a single session is one of convenience, both for the patient, and for the treatment team, since each treatment can last up to 2 hours. However, single fraction stereotactic body radiotherapy to the spine must be evaluated for safety in terms of avoiding spinal cord myelitis or myelopathy, since there is no opportunity to correct for positioning errors, and once radiation has been delivered, any spinal cord sequelae that occurs is likely to be irreversible. Data from our current protocol for 3 fraction stereotactic radiation to the spine has demonstrated that the 95% confidence interval of the probability of developing paralysis is between 0 and 10% based on the Clopper-Pearson analysis of approximately 70 patients treated so far, and no cases of paralysis have been observed to date. We wish to treat patients in a single fraction with stopping rules such that the trial will halt if the probability of paralysis exceeds 1%.

The statistical characteristics of this trial for single session stereotactic radiation to the spine are described below. The primary issues in the trial are safety (proportion of paralysis) and effectiveness (tumor control, pain relief). The trial is intended to test the safety of giving stereotactic radiation in a single session and to determine tumor control based on spinal MRI. The prevalence and severity of spinal pain at pre-treatment baseline, and during longitudinal follow-up will be measured.

SAFETY

The trial will terminate (and a lower dose studied) if the investigator determines that there is evidence of paralysis (Grade 4 motor neuropathy) caused by radiation myelitis and not by tumor progression or spinal cord compression is at a rate of the treatment is greater than 0.01 (1%).

Sixty patients will be enrolled for the safety portion of the trial. The patients will be regularly monitored through follow-up visits for signs and symptoms of neurological toxicity. The probabilities of such termination as a function of the toxicity probability is shown below.

Design of the Trial

----- High -----			
Num Subj	Cont	Pr Quit	Cum Probability Quit
15.	1.	0.00963	0.00963
30.	1.	0.02652	0.03615
45.	2.	0.00247	0.03861

60. 2. 0.00809 0.04670

Properties of the Design Assuming the Null Hypothesis
(p = 0.0100)

Quit If Evidence That $\Theta > H_0$

Prob Event	Prob Quit	Expected N	Expected N Given Quit
0.0100	0.0467	58.73	32.87

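### The pain-relief endpoints have no cut-off for further local treatment at the treated level, so relief that follows such treatment is credited to single-session SBRT

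*Combined protocol and SAP*

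**What the plan says.** Section 7.0 (Criteria for Response) makes the occurrence of complete pain relief, and how long it lasts, the primary efficacy endpoint. Complete relief is an average pain score of zero over two consecutive analysis periods. Partial relief is a 2-point fall in worst pain over two such periods. Time to maximal relief runs from the first day of irradiation "until the lowest pain score for average pain after radiotherapy", with no end date.

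The failure list begins "All the following are considered treatment failures" and has three items: a non-zero score unchanged within 8 weeks, a sustained 2-point rise in the first month, and a fall of at least 2 points followed by a sustained rise of at least 2 on two successive questionnaires. Section 9.0 repeats the failure and relief lists as secondary considerations. It puts ahead of them a responder rule: worst pain moving from 5 or more to 0-4 at 1 month after enrollment.

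On follow-up, section 8.0 says: "Patients will be seen according to the follow up schedule for toxicity monitoring until death"; the only exit is withdrawal of consent. On imaging, section 9.0 says: "Tumor control will be based on spinal MRI showing absence of progression". Section 7.0 records the date of radiological progression, and section 8.0 notes progression on the date it is seen. For the pain-relief rate, section 9.0 says: "All 60 patients entered will be used for this purpose".

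Prior irradiation of the site bars entry (sections 3.0 and 4.0). Nothing in the supplied text says how irradiation, surgery, or augmentation or ablation of that site after SBRT is handled in any analysis.

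**The concern.** A patient whose pain does not respond may go on to another local treatment at the same level. If pain then falls, the written definitions cannot tell that relief from relief produced by the single session. The trial is single-arm and is read against fixed expectations, including 40% complete relief by 6 months and mean durations of 13 weeks (complete) and 24 weeks (some relief). No comparator group shares the effect, and the patients credited are those in whom the single session had not been enough. The complete-relief rate could therefore be overstated, and durations could include time after another treatment.

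Nor does the text say that a patient who has met a failure item is barred from later relief, so one patient could be counted as both.

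**Working it through.** **1. The plan's own figure.** The only design calculation is the paralysis stopping table. An exact binomial recursion over looks at 15, 30, 45 and 60 patients, stopping when events exceed 1, 1, 2 and 2, gives at p = 0.01: 0.00963, 0.02652, 0.00247 and 0.00809, in total 0.0467, as printed. The point made here does not alter it. The 40% expectation is stated without a derivation.

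**2. Endpoint by endpoint.**

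| Endpoint | Basis | Rule after further local treatment | Exposure |
|---|---|---|---|
| Complete relief and its duration (7.0, 9.0) | Average pain score | None | Full; no time window or end rule |
| Partial relief (7.0, 9.0) | Worst pain score | None | Full |
| Time to maximal relief (7.0) | Lowest average pain score | None | Can be dated to a later treatment |
| Responder (9.0) | Worst pain at 1 month | None | Small; only treatment within that month matters |
| Tumor control (7.0, 9.0) | MRI progression, dated when seen | None | Only if the level is treated before progression is documented |

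**3. One patient through the rules.** Take the scheduled contacts (weeks 1, 2, 3, 4 and 8, then month 3) as the analysis periods. Worst pain is 8 at baseline and 7 at weeks 1-4. The level is operated on or re-irradiated in week 6. Worst pain is 3 at week 8 and at month 3.

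- Failure item 1: not met. The change from 8 to 7 already avoids it, which is a looseness of that item and not an effect of the procedure. Had the score stayed at 8 through week 4, the drop to 3 at week 8 would have avoided it instead.
- Failure items 2 and 3: not met, as there is no rise.
- Partial relief: met, by two consecutive scores at least 2 points below baseline, both after the procedure.
- Complete relief: met if average pain is 0 at both contacts. All of its duration then follows the procedure.
- Responder at 1 month: not met (7 is not in 0-4), which is the right answer.

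**4. Size.** Inputs: N = 60 and the 40% expectation (section 9.0). The rate of further local treatment and its success are not in the documents and are assumed below.

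- One patient wrongly credited: 1/60 = 1.67 percentage points.
- True rate 30%: 0.30 × 60 = 18. The expected 40% is 0.40 × 60 = 24. Difference: 6 patients.
- True rate 35%: 0.35 × 60 = 21. Difference from 24: 3 patients.

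Let b be the rate from the single session alone, s the share of the remaining patients given further local treatment, and r the share of those who then become pain-free. The observed rate is b + (1 − b) × s × r.

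| b | s = 5%, r = 50% | s = 30%, r = 80% |
|---|---|---|
| 30% | 0.30 + 0.70 × 0.025 = 31.8% | 0.30 + 0.70 × 0.24 = 46.8% |
| 35% | 0.35 + 0.65 × 0.025 = 36.6% | 0.35 + 0.65 × 0.24 = 50.6% |

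To reach 40%, s × r must be (0.40 − 0.30)/0.70 = 0.143 or (0.40 − 0.35)/0.65 = 0.077.

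**The case against.** Several limits stand.

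- **Responder rule.** A reader might infer that every endpoint is affected. Section 9.0 ranks the 1-month responder rule above the relief lists, and that rule scores the example patient correctly. But section 7.0 names complete relief as primary, and that endpoint is exposed.
- **Tumor control.** A reader might infer that a second treatment can restore lost control. It cannot: progression is dated when seen. The gap is confined to a level treated, for example for pain or instability, before growth appears on MRI.
- **Existing failure items.** A sustained rise before the second treatment can already meet item 3. That does not help a patient who never improved, and the text does not say that failure overrides later relief.
- **Direction.** Time to maximal relief becomes longer when dated to a later treatment, which does not flatter SBRT. That endpoint is misdated, not inflated.
- **Size.** Complete relief requires average pain of zero twice, so few such patients may qualify; the low case above adds under 2 points. A shift of 6 patients is also within sampling error (exact 95% interval for 18/60: 18.8% to 43.2%). Even so, the error runs one way for the relief rates and the interval does not show it.
- **Data capture.** History is taken at each visit and the appendices were not supplied, so a form field may exist. A field is not an analysis rule.

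A stronger reading is that paralysis after a second treatment corrupts the stopping rule. The documents do not support it. The investigator must first find the paralysis "caused by radiation myelitis and not by tumor progression or spinal cord compression". Paralysis from surgery fails that test, and after re-irradiation the protocol fraction has itself contributed to cord dose. Adding one misattributed event by the 30-patient look does raise the stopping probability at p = 0.01 from 0.047 to 0.287, but only by assuming that the event occurs.

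**Conclusion.** The concern holds for partial relief, complete relief and its duration, and time to maximal relief. As written, all four can take their values from scores recorded after another local treatment, and complete relief is the section 7.0 primary efficacy endpoint. It holds for tumor control only where the level is treated before MRI progression. It is minor for the 1-month responder rule and does not extend to the paralysis stopping rule.

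The omission itself is certain from the supplied text. Its size is not: no rate of further local treatment is given, so no point estimate of the bias is justified. What can be said is 1.67 percentage points per patient credited, and 3 or 6 patients to move a true 35% or 30% to 40%. This assumes that all 60 patients form the denominator; with fewer evaluable for pain, each patient counts for more.

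**What to change.** At the contacts already scheduled, record the date and type of any re-irradiation, surgery, or vertebral augmentation or ablation at a treated level. In sections 7.0 and 9.0, state that:

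- such treatment is a pain treatment failure on its date;
- pain scores after that date do not count toward partial relief, complete relief, duration of relief or time to maximal relief;
- failure takes precedence over any later relief.

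Keep MRI progression as the main definition of tumor control. Making every procedure a loss of control would count radiographically stable lesions as failures. Instead, add a sensitivity analysis that censors at the intervention or counts it as loss of control.

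The cost is one extra data item and slightly less favourable relief rates. The sample size and stopping limits do not change. This is an analysis rule only; it proposes nothing about when or whether further treatment is given.
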